**Title: Testing a Brief Substance Misuse Preventative Intervention for Parents/Guardians of
5th-7th Grade Students**

NCT Number: NCT03925220

Study Protocol

Document Date: August 10, 2023; Revised: November 11, 2018

1.0 Purpose of the study:

The purpose of this study is to test the efficacy of a brief, communication-based, substance use preventive intervention for parents of pre/early adolescents. A parallel-group randomized controlled trial (RCT) to test the primary hypotheses that, relative to parents in the comparison condition, parents receiving the intervention, over the study period, will have, on average: 1) greater quality of interactions at meals, 2) a greater number of conversations about substances, and 3) higher quality of content in their conversations with their children about substance use. A companion primary hypothesis will be tested to determine if children of parents randomized to the intervention have fewer intentions and reduced willingness to use substances, reduced affiliation with substance-using peers, and increased negative attitudes and expectancies about substance use in contrast to children of parents in the comparison condition at study follow-up. We will also test a secondary aim's hypothesis, that children of parents assigned to the intervention condition will have a delayed initiation of substance use compared to the comparison condition.

2.0 Background / Literature Review / Rationale for the study:

Universal, family-based substance use preventive interventions have been shown to be efficacious, but programs that have been most effective are resource intensive and require extensive time and effort for program staff and participants. Therefore, an approach to universal substance misuse prevention is needed that is effective, resource-efficient, able to be disseminated easily, and sustainable.

3.0 Participant Population:

PHASE 1:

We propose to enroll parents of pre/early-adolescents (grades 5-7) with their child who live and attend school in Massachusetts.

Inclusion criteria include: 1) the parent must have a child between 5th-7th grades at the start of the project; 2) the parent must be the custodial parent, living with the child at least 50% of the time (as in the case of joint custody); and 3) parental consent and child assent are obtained. If a parent has more than one child that meets these criteria, the target child to participate in the intervention will be randomly chosen by research staff.

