5.2 Sample Size

PHASE 1:

The number of participants from each school will depend upon the number willing and available to participate in each school district, and the total number of participants from all sites combined shall not exceed 1500 (750 parent/child dyads). Note: Sometimes

participants are referred to as parent/child dyads in participant facing materials, but all verbal communication clarifies that a parent/child dyad or pair consists of 2 participants.

PHASE 2:

We will not recruit any new participants for this portion of the study.

Procedures Involved:

PHASE 1:

Eligible, consenting parents and their assenting child will complete baseline assessments related to their family practice of eating meals together, communication skills, parenting styles, and their own substance use. Parents will then be randomly assigned to one of two conditions: 1) intervention, or 2) comparison. Parents and children will then be followed at four follow-up points at 3, 6, 12, and 18 months.

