Participants that do not complete the surveys or videos within the given time period will be followed up with and asked to provide missing data. If changes are made to survey instruments after participants have already received the instrument, study staff will treat this as missing data and will contact participants to obtain the missing data.

A set of questions related to participants' experiences during the COVID-19 pandemic (March 2020-April 2021) will be appended to the end of all currently enrolled participants' next timepoint survey [as of approval from IRB from this submission on 27 Sep 2021]. Both parent and child will be asked to complete questions (6 and 2 additional questions, respectively). Participants have the option to skip any questions they do not feel comfortable responding to. The questions will only be asked once.

In situations where participants express interest in continuing with the study but lack time to complete materials for a specific time point, participants will have the option to complete a shortened survey. They will specifically consent/assent to taking this shortened survey and receiving a \$5 (3- or 6-month) or \$10 (12- or 18-month) Amazon e-gift card. This consent/assent process is completed at the beginning of the shortened survey.

The expected duration of the study is 5 years.

When a participant completes the study, we will complete the following steps:

- Offer the other group's materials to be emailed or mailed to them
- Send them the completion email and request a response to confirm their acknowledgement of completion
- Send them instructions on what to do with the tablet
- Ask them to complete a form which asks for consent to keep their contact information if they have not already completed this form at a previous timepoint

(participants may complete this form at any point during the study) for potential future studies

We will keep all contact information of adult participants for future study purposes who consent to us keeping their information for this purpose. This contact information will be kept in its own Box folder, separate from any data or other study-related files. For those that do not consent to us keeping their contact information, we will delete their contact information after five years after the cessation of the study as per the protocol (Section 17.0 Data Management and Confidentiality).

PHASE 2:

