Participants that are currently enrolled in the study will be contacted and asked to consent to the continued follow-up (i.e. Phase 2) to begin three months after they complete Phase 1's final follow-up point at 18-months (i.e. their first survey for Phase 2 will occur 3 months after Phase 1's 18-month follow-up time point).

Participants that have completed Phase 1 already, will be contacted and asked to consent to start the Phase 2 follow-up immediately.

All eligible, consenting children only will be asked to complete a brief online survey (approximately 5 minutes) every three months for up to two years. There are two different surveys (i.e. "Int" and "Cont") Only one will be administered at each time point and we will switch back and forth at each time point (e.g. first survey will be "int" then at next follow up the "Cont", then "Int", etc.). The "Int" survey will ask about the child's mental health, substance use initiation, willingness to use, intentions to use and peer use, as well as, the frequency of substance use conversations they have with their parent. The "Cont" survey will ask about the child's substance use initiation, the child's perception of body image/weight, child's mental health and other weight-related behavior questions.

PHASE 1:

Instrumentation

- Questionnaires
- Video: Video observation of family meals and parent-child discussions about substance use
- Audio: intervention in-person/video conferenced sessions will be recorded for quality assurance
- Other: height/weight measurement of children

Online Instrumentation

- The online survey engine REDCap will be used to present the surveys.
 - <https://collaborate.tuftsctsi.org/redcap//index.php?action=myprojects>
- Online recruitment agencies will have their own method of distributing the approved screening and eligibility survey to potential participants, such as a Qualtrics or REDCap survey.

- Participants will be able to complete the entire survey if they abstain from answering certain questions.
- Paper surveys are also available.

PHASE 2:

Online Instrumentation

- The online survey engine REDCap will be used to present the surveys. We will use the same database that Phase 1 documents are stored/administered from.
- Participants will be able to complete the entire survey if they abstain from answering certain questions.

5.2 Additional Safeguards for Special Populations:

PHASE 1 & 2:

Children

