Parent/child dyads will be compensated \$60 for completing the baseline assessments, \$60 for the 3-and 6-month follow-up surveys, and \$80 for the 12-and 18-month follow-up surveys. Dyads will also receive an tablet in order to record their family meals and their conversations about SU. They will be able to keep the tablet as compensation if all video recordings are completed at each time point. Monetary compensation will be in the form of either cash or an Amazon gift card.

For participants who complete the Brief Specific Aims Only Survey for a given time point will receive either \$5.00 (3- or 6-month surveys) or \$10.00 (12- or 18-month) Amazon gift card. The Brief Specific Aims Only Survey is approximately 10% the length of the full-length survey; therefore, the compensation is proportional. This is in place of completing the full-length survey for that time point and receiving the usual compensation described above.

Compensation for completion of surveys occurs at each follow-up timepoint. Any participant who withdraws from the study before finishing will keep any compensation up until the point of withdrawal but will not be compensated for study activities they would have completed after the timepoint at which they withdrew.

PHASE 2:

The child will be compensated \$10 in the form of an e-gift card for each survey completed. If all surveys are completed, the child could receive up to \$80 in e-gift cards.

Compensation for completion of surveys occurs at each follow-up timepoint. Any participant who withdraws from the study before finishing will keep any compensation up until the point of withdrawal but will not be compensated for study activities they would have completed after the timepoint at which they withdrew.

11.0 Economic Burden:

PHASE 1:

Participants will be responsible for the cost of travel to any interventionist sessions outside their home. Every effort is made to schedule sessions at a location convenient for the participant (e.g. home, work). All activities can also be completed virtually.

PHASE 2:

There is no economic burden as all surveys will be administered online.

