**NCT Number: NCT03925220**

**Statistical Analysis Plan**

**Document Date: August 10, 2023; Revised: November 11, 2018**

## **Data Analysis Plan**

The scientific rigor of this application is reflected in our preliminary analyses, missing data detection and correction procedures, and our data analytic strategies. First, all forms will be checked for missing data and outliers prior to data entry. Attrition effects will be evaluated by testing whether systematic differences exist between participants who complete the research versus those who drop out. We will also examine any pre-existing differences between the two conditions in demographic composition and all measures collected at baseline. Pre-existing group differences in these variables will be accounted for in subsequent analyses, using baseline scores as covariates. Participants will be included in the analysis if they are randomized (i.e., intention -to-treat).

Participants who are lost to follow-up or drop out can affect the validity of the group comparisons if: 1) the outcome of interest is related to being lost or dropped, and 2) it is differential between groups. The missing data mechanism will be formally tested to determine whether it is Missing Completely at Random (MCAR) or Missing at Random (MAR). For completeness in assessing the effect of missingness, two additional analyses will be conducted: 1) a 'per-protocol' analysis among participants who complete all follow-up surveys; and 2) multiple imputation of five data sets using a discriminant function for binary outcomes and Markov chain Monte Carlo for continuous outcomes, assuming the missing data mechanism is MAR.

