**Aim 1:** To determine the efficacy of the brief intervention on parent outcomes. The proportion of parents who more frequently communicate will be compared between conditions across the follow-up periods using a repeated measures log-binomial regression analysis (via generalized estimating equations; GEE), with an appropriate covariance structure and adjusting for baseline scores. Covariates will be added to the modeled analyses if differences among baseline characteristics are observed. A test for interaction between condition and follow-up point using the above models will assess whether there is a differential intervention effect across time, taking intervention dose delivered and received into account. To assess quality of mealtime interactions, we will first score the videos according to the IFIRS and then analyze the data using repeated measures analysis of covariance (i.e., a linear mixed model) to compare the two conditions across the follow-ups, using an appropriate covariance structure and adjusting for baseline scores. A similar analysis will be used for the summed scores from the FAsTask, which assess the quality of parent-child conversations about SU.

**Aim 2:** To examine the effects of the intervention on child SU beliefs, intentions, and willingness, and affiliation with substance-using peers. We will compare the proportion of children with intentions and willingness to use substances, negative SU attitudes and expectancies, and substance-using peers between conditions across the follow-up periods using a repeated measures log-binomial regression analysis (via GEE), with an appropriate covariance structure and adjusting for baseline scores.

**Secondary Aim 1:** To examine the effects of the intervention on SU initiation. To assess whether children of parents in the intervention condition delay the initiation of SU longer than the comparison condition, we will compare the incidence of initiation using a

discrete-time survival analysis via a complementary log-log regression model, as the date of initiation between follow-up time points may not be known exactly.

Exploratory analyses will be run by race and ethnicity. Because it is known that subgroup analyses have less statistical power than the primary analysis, we will conduct exploratory analyses to determine whether the efficacy of the intervention varies by race and ethnicity, to inform future adaptations.

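### Does the missing last time point in the initiation model (SAP, Secondary Aim 1) leave the trial with two competing answers?

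*SAP*

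**What the plan says.** The SAP's Data Analysis Plan, under Secondary Aim 1, compares the incidence of initiation by discrete-time survival analysis with a "complementary log-log regression model, as the date of initiation between follow-up time points may not be known exactly". It gives no list of waves, no censoring rule and no final time point. The hypothesis in Protocol section 1.0, that "children of parents assigned to the intervention condition will have a delayed initiation of substance use compared to the comparison condition", has no horizon either.

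Under Procedures Involved, Phase 1, the protocol says: "Parents and children will then be followed at four follow-up points at 3, 6, 12, and 18 months". Under Phase 2, families are asked for "consent to the continued follow-up (i.e. Phase 2) to begin three months after they complete" the 18-month point of Phase 1. Children then answer short surveys every three months for at most two years. Two forms alternate. One covers mental health and "substance use initiation, willingness to use, intentions to use and peer use"; the other also asks about initiation. Section 10.0 says under both phases: "Compensation for completion of surveys occurs at each follow-up timepoint".

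The Phase 1 list of steps for a participant who finishes includes: "Offer the other group's materials to be emailed or mailed to them". The SAP's per-protocol set is an "analysis among participants who complete all follow-up surveys", again without saying which phase.

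**The concern.** The protocol applies the word follow-up to both phases, and both Phase 2 forms measure initiation. The Secondary Aim 1 model could therefore be read as ending at month 18 or as running through Phase 2. These are not the same comparison. Up to month 18 it is intervention against comparison. After it, if the materials are offered when Phase 1 ends, it is early full intervention against comparison plus a delayed offer, in a subset that consented again. A single ratio over the whole period averages the two. If someone saw both results and chose between them, the nominal 5% error rate would not hold, and a weaker long-run ratio could mean a fading effect, selective entry to Phase 2 or the offer itself. The same loose term appears in Aim 2 and in the per-protocol set.

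**Working it through.** The documents give no alpha, power, initiation rate or event count, so there is no planned figure to reproduce. The check has three parts.

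**1. Schedule (Protocol, Procedures Involved and section 10.0).** Phase 2 surveys: 24 months / 3 = 8, which agrees with $80 / $10 = 8. First survey: 18 + 3 = month 21. Last: 21 + 7 × 3 = month 42. The model has 4 intervals on the short reading and 4 + 8 = 12 on the long one. Month 42 is not a ceiling: children who had finished Phase 1 before Phase 2 opened start on consent and can run later.

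**2. What follow-up means in the SAP.**
- The SAP does not mention Phase 2.
- Aim 1 of the SAP analyses scored meal videos across the follow-ups. Protocol section 12.0 says Phase 2 has no recordings, so that use of the word can only mean Phase 1.
- Aim 2 includes attitudes and expectancies, which neither Phase 2 form is said to cover.
- Dating the offer at month 18 means reading study completion as the end of Phase 1. On that reading the study's follow-up most naturally ends there too.

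**3. What is at stake if Phase 2 were pooled.** Assumptions, none from the documents: 375 per arm (the 750-dyad ceiling halved), constant hazard, no dropout before month 18, 50% to 100% of children entering Phase 2, uptake p of the materials in the comparison arm, and a share f of the log effect carried by the materials. The complementary log-log model is fitted to expected counts over intervals ending at months 3, 6, 12, 18, 21, …, 42.

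*No true effect.* The two test statistics have correlation SE(42)/SE(18) = 0.67 to 0.82. P(either |z| > 1.96) = 0.077 to 0.085 for 5% to 25% initiation by month 18. The offer plays no part in this figure.

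*True ratio 0.70, 15% comparison-arm initiation by month 18.* The 18-month model gives 0.70 with power 0.41 in every row.

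| Phase 2 entry | f | p | 42-month ratio | Power | Verdicts differ |
|---|---|---|---|---|---|
| 100% | any | 0 | 0.70 | | 0.36 |
| 100% | 0.5 | 0.25 | 0.716 | 0.66 | 0.33 |
| 100% | 0.5 | 0.50 | 0.732 | 0.59 | 0.30 |
| 100% | 1 | 0.50 | 0.76 | 0.47 | 0.26 |
| 50% | any | 0 | 0.70 | | 0.25 |
| 50% | 1 | 0.50 | 0.741 | 0.44 | 0.20 |

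With 5% initiation, verdicts differ in 0.16 to 0.24 of trials at zero uptake and in 0.13 to 0.22 at 25% to 50% uptake. At both initiation rates disagreement is largest when nobody takes the materials. It arises because one model has many more events than the other.

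*The offer's own effect.* The ratio within Phase 2 is HR / ((1 − p) + p × HR^f). For HR = 0.70, p = 0.5, f = 1: 0.70 / (0.5 + 0.35) = 0.82. Pooled to month 42, a true 0.70 becomes 0.71 to 0.76 at 25% to 50% uptake. In the extreme case of no difference between arms after month 18, with an assumed control hazard of 1% to 2% per quarter growing by 0% to 10%, it becomes about 0.86 to 0.91. A true ratio of 1.0 stays 1.0, so the offer cannot create an effect.

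**The case for a change.** The strongest case for a change is that month 18 is inferred and nowhere stated. The protocol and SAP carry the same dates, and that protocol describes Phase 2 with initiation in every survey, so the SAP's silence cannot be put down to age. Initiation is the behaviour the programme exists to prevent, a sentence would be cheap, and the choice loses credibility once results by arm are known. That much stands: the horizon is unstated, and no part of either document assigns the Phase 2 initiation data to an analysis.

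The rest is weaker. It might be argued that Phase 2 initiation items can only serve the secondary hypothesis, because no other is stated. But one Phase 2 form also asks about body image and weight-related behaviour, which serve no stated hypothesis. Phase 2 excludes parents who declined contact for other studies, and section 13.0 presents its value as informing implementation. Phase 2 data need not belong to Secondary Aim 1.

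The per-protocol worry needs the unlikely reading too. If each survey is completed independently with probability 0.90 to 0.97, four are completed by 0.90^4 = 66% to 0.97^4 = 89%, and twelve by 0.90^12 = 28% to 0.97^12 = 69%. The drop is large, but only if a separately consented extension is counted as part of the protocol to be completed.

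**Conclusion.** No change to the plan is needed. This is a missing detail that an analyst fills sensibly: Secondary Aim 1 runs over the four Phase 1 points to month 18, and any Phase 2 initiation analysis is a separate extension. On that reading the offer of materials falls after the last interval and cannot affect the result.

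The choice between horizons is a fair trade-off. Month 18 keeps one clean contrast with power 0.41 in the illustration. Pooling to month 42 raises power to 0.44 to 0.66 at 25% to 50% uptake, at the price of a ratio that mixes two contrasts and depends on renewed consent. It can also lose power: at full uptake with full effect it falls to 0.24 to 0.30. The offer makes neither comparison by randomized arm invalid, and splitting the model at month 18 or recording receipt dates would change nothing in the 18-month analysis.

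The roughly 8% type I error requires a post hoc choice of horizon, which the documents give no reason to expect. All power, ratio and disagreement figures rest on assumed initiation, effect, uptake and Phase 2 entry. The conclusion rests instead on the text, with one inference: that the offer is made when Phase 1 ends, as its place in the Phase 1 list beside the tablet step suggests.
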